6.6.2 Pairing Scheme

- 1) All YSI^{TM*} collected will be presented. Descriptive analyses will include all YSI^{TM*} values, such as those less than (<) 40 mg/dL, or greater than (>) 400 mg/dL as long as GuardianTM Sensor (3) values are greater than or equal to (≥) 40 mg/dL or less than or equal to (≤) 400 mg/dL.
- 2) Reference glucose values (YSI^{TM*} values) will be paired with the closest GuardianTM Sensor (3) value between [0, 5) minutes.
- 3) The primary Guardian™ Sensor (3) will be used as a reference for precision analysis and the pairing scheme will be [0, 5) minutes.

6.6.3 YSITM* Retention

All YSI^{TM*} values will be captured and retained in OC-RDC database. However, if the absolute relative difference between Result A (black) and Result B (white) is greater than (>) 5%, the YSI^{TM*} values will not be included in the analysis dataset.

- (1) At first, delete observations which were identified as deletion according to "deletion flag" collected in OC-RDC database;
- (2) Calculate absolute relative difference between Result A (black) and Result B (white) by the formula: Result A (black) Result B (white) Result A (black) *100%. If the ARD% is greater than 5%, then this observation will be deleted.
 - (3) The mean of Result A (black) and Result B (white) will be used in paired data analysis finally.

6.6.4 Sensor Data Retention

All collected sensor glucose data from the study will be analyzed. It includes, but is not limited to, sensor glucose data reprocessed with additional MeterBGs collected by patients.

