5.2.5. Subject Feedback

Descriptive summary will be used to characterize study questionnaire results. The questionnaire will use a Likert scale rating to assess their GuardianTM Sensor (3) experience.

6. Study Design

This study is a multi-center, prospective single-arm design without controls. Up to 72 subjects will be enrolled in order to have approximately 60 subjects complete the study. Three investigational centers in China will be used during this study.

During the study, each subject will be randomly assigned to one day of the Yellow Springs Instrument (YSI™*) frequent sample testing (FST) (Day 1, 3-5, or 7). Subjects will wear two Guardian™ Sensor (3)s each connected to a Guardian™ Connect transmitter for approximately 7 days (one which will be paired to the Guardian Connect app and the other will function as a glucose recorder.).

The Guardian Sensor (3)s will be worn in the abdomen area and self-inserted by the subject on same side or opposite sides.

On the evening prior to FST, subjects will be asked to fast for approximately 12 hours and adjust their insulin and medications according to routine care (for example as they would do for fasting lipid panel). Subjects may fast for shorter period of time **based on investigator discretion.**

The subject should be in fasting status upon arrival at hospital to start FST process. **The feeding protocol may be modified based on investigator discretion.**

The duration of FST will be approximately 7 hours.

During the study, subjects will continue with their current diabetes regimen independent of the study devices.

CIP320 Clinical Investigation Plan 10768467DOC Version C Page 25 of 97 Medtronic

Subjects will be instructed by the investigational center that they are not to use the study devices (except for the CONTOUR^{TM*} study meter) for the management of their diabetes. The CONTOUR^{TM*} study meter may be used for treatment decisions and calibration of GuardianTM Sensor (3).

Calibration at Home: Calibration at home will be required to be 3-4 times spread throughout the day for the GuardianTM Connect app.

Calibration should also be performed if the Guardian™ Connect app prompts for calibration (i.e., Smart calibration feature). NOTE: Subject will be instructed to minimize the delay time between prompt and calibration.

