Fingerstick Testing: Fingerstick testing will be recommended to be a minimum of 4 times spread throughout the day. Subjects should test prior to and following meals and at bedtime.

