7.1.4. Guardian™ Connect Transmitter (MMT-7821)

The Guardian™ Connect transmitter (MMT-7821) is an investigational device that has a similar housing and sensor interface as the MiniLink transmitter (it has a lockout feature to allow it to connect to Guardian™ Sensor (3) and prevent connection to other Medtronic glucose sensors, e.g. Sof-Sensor). However, the internal electronics and firmware of the Guardian™ Connect transmitter are new. Like the MiniLink transmitter, the Guardian™ Connect transmitter reads the electronic signal generated by the sensor. In addition, the transmitter contains a custom Application Specific Integrated Circuit (ASIC), which enables Electrochemical Impedance Spectroscopy (EIS). The EIS measurements are used as diagnostics for the sensor, which are incorporated into the sensor calibration logic.

In addition, the transmitter also contains the sensor calibration algorithm which converts the sensor signal to a sensor glucose value using BG values from a meter (manually entered by subject into the Guardian™ Connect app and relayed to the transmitter for calibration). The transmitter transmits the calculated glucose data to the Guardian™ Connect app via 2.4GHz RF technology (Bluetooth Low Energy or BLE). The new algorithm is designed to improve and optimize performance when paired with the Guardian™ Sensor (3). Some elements of the new calibration logic include prompting the user to calibrate when needed, referred to as "Smart Cal" in addition to scheduled time-based calibration requirements.

In this study, one of the GuardianTM Connect transmitter will be connected with a GuardianTM Sensor (3) which will be paired to an iOS device loaded with the GuardianTM Connect app. The GuardianTM Connect transmitter will also store recorded data and at the end of the study, it will be downloaded.

The Guardian[™] Connect transmitter is intended as a single patient, multi-use device.

CIP320 Clinical Investigation Plan 10768467DOC Version C Page 28 of 97 Medtronic

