14.8. General Considerations for Data Analysis

14.8.1. Data Collection

Primary endpoint and other descriptive endpoints will be based on real-time data collected from primary sensor. Precision analysis will be based on data collected from both sensors.

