14.10.2. Precision Analysis

Precision analysis will be performed for the two sensors worn by the same subject. Data from the primary GuardianTM Sensor (3) will be used as a reference. Data from sensor functioned as recorder will be reanalyzed using the exact calibration SMBG used for the primary sensor.

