6.6 General Considerations for Data Analysis

6.6.1 Data Collection

Analysis data source: The analysis of primary endpoints, other descriptive endpoints and simulation alert calculation will be based on both Oracle Remote Data Capture (RDC) database and external device dataset (collected sensor glucose data). The detailed specification of variables from external device data are as following:

- SG: Raw Sensor Glucose Reading
- PSGV: Predicted Sensor Glucose Reading
- SBG: Sensor Blood Glucose (values below 40 display as 40, values above 400 display as 400) elaborated below
- ROC: Rate of Change of SG
- ISIG: Interstitial Signal
- FORCALBG: Used in Calibration

The value "511" in the SG and PSGV column indicates "null". The SBG column will display saturated values of 40 if the reading was displayed as "Low" (i.e. if SG < 40 mg/dL) or 400 if the reading was "High" (i.e. if SG > 400 mg/dL) while the SG column will display 511. SG value of 40 is indicated when SG and SBG columns are equal to 40, and same for 400. SG column is used to generate the numerical calculation for sensor performance. SBG is used for alert analysis and sensor life analysis. PSGV and ROC columns are used for alert analysis.

In addition, primary endpoints, other descriptive endpoints, and functional sensor life time will be based on real-time data collected from primary sensor. Precision analysis will be based on data collected from both sensors.

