7.6 Primary Endpoints

Detailed analyses for four primary endpoints are as following:

- 1a) For the 20/20% agreement rate analysis, the analyses based on measurement level will be provided. Both the approximate normal distribution method and Clopper-Pearson method will be used to estimate primary endpoint based on measurement level. The 97.5% lower confidence limit of the agreement rate will be tested against corresponding threshold.
- 1b) Sensor values from primary sensor will be compared to YSI^{TM*} plasma glucose values during YSI^{TM*} FSTs. A mean rate in Zone A+B of Consensus Error Grid between Guardian Sensor (3) values and YSI^{TM*} plasma glucose values during YSI^{TM*} FST days.
- 1c) Sensor values from primary sensor will be compared to YSI^{TM*} plasma glucose values during YSI^{TM*} FSTs. A mean rate in Zone A+B of Clarke Error Grid between Guardian Sensor (3) values and

YSITM* plasma glucose values during YSITM* FST days.

1d) Sensor values from primary sensor will be compared to YSI^{TM*} plasma glucose values during YSI^{TM*} FSTs. A mean absolute relative difference (MARD) between Guardian Sensor (3) values and YSI^{TM*} plasma glucose values during YSI^{TM*} FST days.

At 1b) and 1c) evaluation criteria, both the approximate normal distribution method and Clopper-Pearson method will be used to analysis primary endpoint based on measurement level. The 97.5% lower confidence limit of the mean rate in Zone A+B of Consensus Error Grid, and the mean rate in Zone A+B of Clarke Error Grid will be tested against corresponding threshold, respectively.

At 1d) evaluation criteria, one sample T test will be used based on subject level and the 97.5% upper confidence limit of the MARD will be tested against corresponding threshold.

The study will be considered as a success only when the four evaluation criteria (1a), 1b), 1c), and 1d)) meet the pre-defined thresholds.

The analysis of primary endpoint will be performed on both the FAS^{#2} and PPS; and will be based on the available paired data only according to pairing scheme after considering YSI^{TM*} retention and sensor data retention principle.

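### The SAP gives two conflicting rules for which sensor values enter the four primary tests: real-time values only, or all values including reprocessed ones

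*SAP*

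**What the plan says.** Two statements limit the primary endpoints to real-time data.

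- Protocol 14.8.1: "Primary endpoint and other descriptive endpoints will be based on real-time data collected from primary sensor".
- SAP 6.6.1: "primary endpoints, other descriptive endpoints, and functional sensor life time will be based on real-time data collected from primary sensor".

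SAP 7.6, which sets out the pass/fail analysis, says that the analysis uses available paired data under the pairing scheme, after considering the YSI "retention and sensor data retention principle". The only section that matches the sensor part of this reference is SAP 6.6.4, Sensor Data Retention. Its first sentence has all collected sensor glucose data from the study analysed. Its second reads: "It includes, but is not limited to, sensor glucose data reprocessed with additional MeterBGs collected by patients".

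The only reprocessing that the protocol describes is narrower. Section 14.10.2, on precision, says: "Data from sensor functioned as recorder will be reanalyzed using the exact calibration SMBG used for the primary sensor". The SAP's own precision section (numbered 7.7.2) does not repeat this limit. SAP 7.13 lists two changes to the planned analysis, the dropped Continuous Error Grid and the replaced Gail-Simon test. Neither concerns reprocessed data.

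**The concern.** According to protocol 7.1.4, the transmitter "converts the sensor signal to a sensor glucose value using BG values from a meter"; those readings are entered by the subject in the app. Recalculating with other readings gives values that the system did not calculate or show during wear. The primary objective is accuracy in use with the Guardian Connect System, so a test on reprocessed values would answer a different question. Accuracy on such values could differ from real-time accuracy and might plausibly be better, but the documents do not show this.

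The study is single-arm and judged against fixed thresholds, so the analysis dataset is a main safeguard and has to be fixed in advance. With both rules in the SAP, the choice could be made after the results are known. The sensitivity analyses are exposed as well: SAP 6.5 treats a YSI value without a paired sensor value as missing, and reprocessing could change which YSI values fall into that group.

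**Working it through.** **1. The rules side by side**

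| Place | Applies to | Sensor values |
|---|---|---|
| Protocol 14.8.1 | Primary and other descriptive endpoints | Real-time, primary sensor |
| SAP 6.6.1 | The same, plus functional sensor life | Real-time, primary sensor |
| SAP 6.6.4 | No endpoint or sensor named or exempted | All collected, including reprocessed |
| SAP 7.6 | Primary endpoints 1a to 1d | Refers to the retention principle (6.6.4) |
| Protocol 14.10.2 | Precision only | Recorder sensor, with the primary sensor's calibration readings |

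The reference in 7.6 covers the primary endpoint as a whole, so it reaches all four criteria. There is a second link. SAP 6.6.1 describes the external device dataset as the collected sensor glucose data, the same term that 6.6.4 extends to reprocessed values. It takes performance from the SG column without saying whether that column comes from the transmitter download or from a reprocessed file.

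**2. The plan's own figures (SAP 6.2, one-sided alpha 0.025)**

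- 1a, 0.65 against 0.60: the printed formula gives n = 741.6, so 742 points. Power at 1,200 is 94.7%.
- 1b and 1c, 0.95 against 0.90: n = 238.03, so 239 points. Power at 1,200 is above 99.9%.
- 1d, 18 against 20 with SD 5: n = (1.96 + 0.845)² × 25 / 4 = 49.2, so 50 subjects. Power at 60 is 87.3% by z and 86.2% by t.

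The stated power is reproduced. No figure in the plan is disputed here.

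**3. How far the planned result lies from each threshold**

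Pairs are taken as independent, as the plan takes them.

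- 1a: the test needs (k/1200 − 0.60) / √(0.24/1200) > 1.96, so k > 753.3 and the smallest passing count is 754 (62.8%). Clopper-Pearson also gives 754; the normal interval with the observed variance gives 753. The planned result is 0.65 × 1,200 = 780. Falling to 753 takes 780 − 753 = 27 pairs, or 27/1,200 = 2.25%.
- 1b and 1c: (k/1200 − 0.90) / √(0.09/1200) > 1.96 gives k > 1,100.4, so 1,101. Clopper-Pearson gives 1,101 and the normal interval 1,099. The planned result is 0.95 × 1,200 = 1,140. Falling to 1,100 takes 40 pairs.
- 1d: the observed MARD must be below 20 − t(0.975, 59) × 5/√60 = 18.71. The planned value is 18, a distance of 0.71 points.

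For 1a, the chance of passing at 1,200 points is 29.1% at a true agreement rate of 62%, 56.5% at 63%, 81.2% at 64% and 94.7% at 65%. If the two datasets differed by one or two percentage points in this region, the choice between them could decide the test.

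**4. Are there additional readings to reprocess with?**

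Protocol Section 6 states: "Calibration at home will be required to be 3-4 times spread throughout the day". On fingersticks it states: "Subjects should test prior to and following meals and at bedtime", with a recommended minimum of 4 tests a day. Assume three meals a day, and that calibrations use readings from among these tests.

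- Full schedule: 3 × 2 + 1 = 7 readings. Less 3 to 4 calibrations, 3 to 4 a day are additional.
- Minimum schedule: 4 readings. Less 3 to 4 calibrations, 0 to 1 a day is additional.

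Such readings can therefore exist, but the SAP does not say which of them would be used.

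**The case against.** The strongest reply is that the rules can be read together. SAP 6.6.1 is the specific rule for the primary endpoints and repeats the protocol, whereas 6.6.4 is general and names no endpoint. Reprocessed data have other uses: the recorder sensor is not paired to the app and appears to need later calibration, and the study also collects data to model accuracy with other pump systems. Pairing each YSI value with the closest sensor value presupposes a single stream. Protocol 14.14 requires departures from the original statistical plan to be reported. The table shells in the SAP appendix, which are not in the text available here, might name the source.

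This is a plausible account of what was intended, but it does not remove the conflict. No sentence gives 6.6.1 precedence, and 7.6 expressly brings the retention principle into the pass/fail analysis. Protocol 14.10.2 cannot be what 6.6.4 describes, because it uses exactly the primary sensor's calibration readings and 6.6.4 uses additional ones. The reporting duty in 14.14 helps less than it seems to, since an analyst following 6.6.4 could say that the SAP was followed.

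Two parts of the reply stand. The margins above show distance to a threshold and would be the same for any doubt about the primary data. The omission from the SAP's precision section has no bearing on pass/fail by itself.

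**Conclusion.** The concern holds. The SAP states two rules for the primary dataset that do not agree, and the conflict reaches all four criteria. It does not clearly order reprocessed values into 1a to 1d; it leaves both readings open. The effect on the result cannot be sized from the documents, in amount or direction, and none is claimed. The distances of 27 pairs, 40 pairs and 0.71 points rest on the planned rates, 1,200 independent pairs, 60 subjects and an SD of 5. They show only that a modest difference between datasets could decide a test if the results come out near plan. This should be corrected before the sensor data are analysed.

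**What to change.** Change the SAP as follows.

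- **7.6:** state that 1a to 1d use only sensor glucose values calculated in real time by the primary sensor's transmitter during the FST.
- **6.6.1:** state that the SG column for 1a to 1d comes from the transmitter download and not from a reprocessed file.
- **6.6.4:** limit reprocessed values to the recorder-sensor precision analysis, with the primary sensor's calibration readings, and to the characterisation of other systems.
- **Precision section (7.7.2):** restore the reprocessing rule from protocol 14.10.2.
- **7.13:** if an accuracy analysis on reprocessed values is wanted, list it here and label it descriptive.

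The cost is a few sentences. Protocol 14.8.1 already specifies real-time data, so no amendment is needed, and the transmitter data are already downloaded at Visit 5. If real-time values were always intended, the analysis itself does not change.

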6.7 Center (Site) Pooling

Data will be pooled for analysis.

6.8 Adjustments for Multiple Comparisons

No adjustments will be made.

6.9 Significance Level and Statistical Analysis Software

For the statistical analysis of the primary endpoint, the level of significance will be set at one-sided 0.025. The level of significance of tests performed on other indicators will be set at two-sided 0.05 level (expect special cases). SAS® 9.4 statistical software and R3.5.2 are applied for statistical analysis.

7. Indicators and Statistical Analysis Methods

7.1 Subject Disposition

The number of subjects enrolled in the study will be presented. The reasons for discontinuing prior to study completion will be summarized.

Version: V1.0

(1) Subjects Enrolled: Subjects who were enrolled in study.

- (2) Screening Failure: The subject did not meet eligibility criteria on visit 1 and did not enter visit 2: random assignment. (Does the subject meet all inclusion criteria, no exclusion criteria, and randomization conditions collected in CRF was "No").
- (3) Subjects Randomly Assigned FST: The subject entered visit 2: random assignment. (Does the subject meet all inclusion criteria, no exclusion criteria, and randomization conditions collected in CRF was "Yes").
- (4) Subjects entering FST: The subject inserted Guardian Sensor successfully and entered visit 4: FST with YSI^{TM*}. (This item is determined based on the subjects' YSI^{TM*} information).
- (5) Subjects completing the Study: Subjects completing Study: The subject completed the last visit. (This item is determined by the section study exit collected in CRF).
- (6) Subjects discontinuing from the study: The subject did not complete the last visit. (This item is determined by the section study exit collected in CRF).

7.2 Subject Demographics and Baseline Characteristics

Subject demographics and characteristics, including age, gender, race, ethnicity, medical diagnosis, height, weight, BMI, CGM experience, diabetes type, pregnancy test result, baseline Hct and baseline A1C will be summarized by descriptive statistics (mean, standard deviation, minimum, median, and maximum) for continuous variables and by counts and percentages for categorical variables.

```
Age = (Informed Consent Date - Date of Birth) / 365.25;

BMI = Weight (kg) / (Height (m))^{2}.
```

7.3 Sensor Disposition

The number of Guardian[™] Sensor (3) insertions and Guardian[™] Sensor (3) removals for every subject enrolled in the study will be presented.

A descriptive analysis of Guardian[™] Sensor (3) disposition including Guardian[™] Sensor (3) dislodgement and reasons why it dislodged will be included in the Final Report. Guardian[™] Sensor (3) insertion and removals will be characterized by the following:

- Duration of Guardian[™] Sensor (3) wear by investigational center subject report
- The number and percentage of Guardian™ Sensor (3)s remaining in place at study end
- Reason for removal: for example, scheduled removal, companion sensor removal, early removal

Version: V1.0

The functional life of the primary Guardian[™] Sensor (3) will also be characterized. The duration of Guardian[™] Sensor (3) performance from the time of first valid Interstitial Signal (ISIG) to the time of

last available sensor value will be summarized by descriptive statistics (mean, standard deviation, minimum, median, and maximum) and described with Kaplan-Meier curves as well.

For the duration of GuardianTM Sensor analysis, both the physical sensor life time and functional sensor life time based on sensor level will be provided. The corresponding calculation methods are as following:

- (1) Physical sensor life time (hours) = (Removal time-Insertion time) /3600, the insertion time and removal time collected in OC-RDC database.
- (2) Functional sensor life time (hours): The analysis data collected in Guardian™ Sensor external database. Related calculation method is as following:
- 1) Find the first valid Interstitial Signal (ISIG) value (i.e. first ISIG after connection indicator), and its corresponding time will be considered as beginning time.
 - 2) Find the last available Sensor value, and its corresponding time will be considered as ending time.
 - 3) Functional sensor life time (hours) = (Ending time- Beginning time) /3600.

7.4 Treatment Characteristics

The total number of YSI^{TM*} collected and deleted will be calculated. In addition, the detailed reason for YSI^{TM*} deletion will also be provided.

7.5 Interim Analyses

Not Applicable.

7.6 Primary Endpoints

Detailed analyses for four primary endpoints are as following:

- 1a) For the 20/20% agreement rate analysis, the analyses based on measurement level will be provided. Both the approximate normal distribution method and Clopper-Pearson method will be used to estimate primary endpoint based on measurement level. The 97.5% lower confidence limit of the agreement rate will be tested against corresponding threshold.
- 1b) Sensor values from primary sensor will be compared to YSI^{TM*} plasma glucose values during YSI^{TM*} FSTs. A mean rate in Zone A+B of Consensus Error Grid between Guardian Sensor (3) values and YSI^{TM*} plasma glucose values during YSI^{TM*} FST days.
- 1c) Sensor values from primary sensor will be compared to YSI^{TM*} plasma glucose values during YSI^{TM*} FSTs. A mean rate in Zone A+B of Clarke Error Grid between Guardian Sensor (3) values and

YSITM* plasma glucose values during YSITM* FST days.

1d) Sensor values from primary sensor will be compared to YSI^{TM*} plasma glucose values during YSI^{TM*} FSTs. A mean absolute relative difference (MARD) between Guardian Sensor (3) values and YSI^{TM*} plasma glucose values during YSI^{TM*} FST days.

At 1b) and 1c) evaluation criteria, both the approximate normal distribution method and Clopper-Pearson method will be used to analysis primary endpoint based on measurement level. The 97.5% lower confidence limit of the mean rate in Zone A+B of Consensus Error Grid, and the mean rate in Zone A+B of Clarke Error Grid will be tested against corresponding threshold, respectively.

At 1d) evaluation criteria, one sample T test will be used based on subject level and the 97.5% upper confidence limit of the MARD will be tested against corresponding threshold.

The study will be considered as a success only when the four evaluation criteria (1a), 1b), 1c), and 1d)) meet the pre-defined thresholds.

The analysis of primary endpoint will be performed on both the FAS^{#2} and PPS; and will be based on the available paired data only according to pairing scheme after considering YSI^{TM*} retention and sensor data retention principle.

